## 2.4 SCIENTIFIC BACKGROUND

Acute kidney injury (AKI) is a serious complication that is independently associated with poor outcomes [1, 2]. Approximately one in five patients with non-severe sepsis develops AKI [3], which increases to two-thirds in critically ill patients. About 50% of ICU patients with AKI die (4-12), and those who survive an episode of AKI have a higher risk of progressing to chronic kidney disease (CKD). Currently, there are few pharmacological therapeutic options available to prevent or treat AKI, and management is limited to alleviating hemodynamic and toxic renal lesions. support measures, such as dialysis.

Iron deficiency occurs in up to 30% of hospitalized patients and has been linked to worse clinical evolution, even in the absence of anemia. This iron deficiency is worse even when anemia figures are reached. It has been documented that critically ill patients develop anemia as part of the process of their pathology. It has been seen that during processes of exacerbation of pathologies such as heart failure, the administration of intravenous iron avoids the probability of hospitalization and clinical evolution (13-16). It has been shown that in DRA there is mitochondrial dysfunction (17), specifically in the renal tubule where the greatest amount of mitochondria is concentrated,

Version 2.0, 29 June 2023

Effect of intravenous iron repletion on renal function in patients with iron deficiency and acute kidney injury, clinical trial. June 2023, HCG/CEI-1232/22

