### 2.5 OBJECTIVES

#### **Primary objective:**

The endpoint of interest was the proportion of patients meeting one or more criteria for Major Adverse Kidney Events within 30 days (MAKE30): in-hospital mortality; receipt of new RRT; or persistent renal dysfunction.

In hospital mortality was defined as death from any cause prior to hospital discharge censored at 30 days after ICU admission. Receipt of new RRT was defined as receipt of any modality of RRT between ICU admission and the first of (1) hospital discharge or (2) 30 days in a patient not known to have received RRT prior to ICU admission. Persistent renal dysfunction was defined as a final serum creatinine value before hospital discharge (censored at 30 days after enrollment) that was  $\geq 200\%$  of the baseline creatinine value.

And will be evaluated at 60 and 90 days.

**Secondary objectives:** all the following will be at hospital discharge and 28 days after hospital discharge between the intervention group (iron replacement) compared to the control group (placebo).

- ferritin value, (pg/dL)
- transferrin saturation (%)
- Hemoglobin (g/dL)
- serum creatinine (mg/dL)
- start of renal support therapy (any type of renal support such as: intermittent hemodialysis, peritoneal dialysis or continuous therapies)
- recovery of renal function, considered as a decrease in serum creatinine and approaching  $<0.3\text{mg/dL}$  of basal creatinine
- death

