## 2. DESIGN OF THE STUDY

Randomized placebo-controlled clinical trial, randomization method in blocks of 5 by frequency of occurrence. In patients with acute kidney injury, they will be randomized to receive the administration of intravenous iron dextran in a single exhibition according to the Mg provided by the Virizzi formula compared to placebo.

The sample size determined 55 patients per group, with a standard deviation of 1.5.

$$n = [(Z_{\alpha/2} + Z_{\beta})^2 \times \{2(\sigma)^2\}] / (\mu_1 - \mu_2)^2$$
$$n = [(1.96 + 0.84)^2 \times \{2(1.5)^2\}] / (10.8 - 10)^2$$
$$n = 55,125$$

n = sample size required in each group  $\mu_1 - \mu_2 =$   
clinically significant difference = 0.8 or = standard  
deviation = 1.5

$Z_{\alpha/2}$ : 1.96

$Z_{\beta}$ : 0.84

Version 2.0, 29 June 2023

Effect of intravenous iron repletion on renal function in patients with iron deficiency and acute kidney injury, clinical trial. June 2023, HCG/CEI-1232/22

[name] [contact], [name] GUADALAJARA, JAL

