# Old Civil Hospital of Guadalajara

## "FRAY ANTONIO MAYOR"

Teaching Subdirectorato  
Research Coordination

urine. The test will be presented in accordance with the CONSORT 2010 explanation and elaboration guide. Continuous variables will be presented as mean (SD) when they are normally distributed or as medians (interquartile range [IQR]) in the case of abnormal distribution, following the test Shapiro-Wilk. One way ANOVA was used to compare differences between groups. Categorical variables expressed as proportions will be compared with Fisher's  $\chi^2$  test or the exact test, as appropriate. For the rest of the tests, p values were two-tailed;  $p < 0.05$  will be considered statistically significant. Statistical analysis and graphics will be performed with the statistical software MedCalc (Ostend, Belgium, see 19.1.3).

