### 4.1 INCLUSION AND EXCLUSION CRITERIA

#### criteria of **inclusion**:

Hospitalized patients with ARD, will be defined as the diagnosis using the KDIGO criteria of serum creatinine (Cr); Patients with AKI  $> 18$  and  $< 85$  years, baseline creatinine  $< 2$  mg/dL and with written informed consent will be included.

Iron deficiency according to the criteria of the 2: serum iron  $< 13$  ng/dL, transferrin saturation  $< 20\%$ .

Version 2.0, 29 June 2023

Effect of intravenous iron repletion on renal function in patients with iron deficiency and acute kidney injury, clinical trial. June 2023, HCG/CEI-1232/22

[name] [contact], [name] GUADALAJARA, JAL

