## 4.2 VARIABLES UNDER STUDY

Exposure variable is the administration of iron dextran in an infusion bolus as a loading strategy.  
Dependent variables will be the value of renal function by eGFR, hemoglobin, iron deficiency, renal function and safety parameters.

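### The only sample-size calculation is for a difference in means of an unnamed variable, so its 80% power does not apply to the primary MAKE30 proportion

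*Protocol*

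**What the plan says.** Protocol, 2.5 Objectives, sets one primary endpoint: "The endpoint of interest was the proportion of patients meeting one or more criteria for Major Adverse Kidney Events within 30 days (MAKE30"), a composite of in-hospital death, new renal replacement therapy and persistent renal dysfunction. It is a yes/no outcome for each patient.

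Protocol, 2. Design of the Study, holds the only sample-size calculation: "The sample size determined 55 patients per group, with a standard deviation of 1.5". It uses the two-means formula with means 10.8 and 10, a "clinically significant difference = 0.8", Z_alpha/2 = 1.96 and Z_beta = 0.84. Neither the variable nor its unit is given.

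The statistical paragraph at the end of that section says: "Categorical variables expressed as proportions will be compared with Fisher's" test or chi-square, as appropriate, two-tailed at 0.05.

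Section 4.2 lists the dependent variables: "Dependent variables will be the value of renal function by eGFR, hemoglobin, iron deficiency, renal function and safety parameters". Hemoglobin in g/dL is also a secondary objective in 2.5 and part of the stated purpose in 2.1.

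**The concern.** A two-means formula has no place for a proportion, so whatever variable has an SD of 1.5, it is not MAKE30. The values 10 and 10.8 would suit hemoglobin in g/dL, but that is an inference, and the point does not depend on it.

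The Protocol presents 55 per group as the size of the trial without tying it to any outcome. A reader can therefore take it that the primary comparison has 80% power. If true power for plausible effects is much lower, a non-significant MAKE30 result is likely even when iron helps. With no detectable difference on record, such a result could be read as no renal effect of iron.

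**Working it through.** **1. The plan's own figure.** Inputs from Design of the Study: Z values 1.96 and 0.84, SD 1.5, difference 10.8 − 10 = 0.8.

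n = (1.96 + 0.84)² × 2 × 1.5² / 0.8² = 7.84 × 4.5 / 0.64 = 55.125 per group.

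The figure reproduces (strictly it rounds up to 56). Power at 55 per group is 79.9% for a mean difference of 0.8 with SD 1.5, and only for that.

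**2. Inputs for MAKE30.** n = 55 per group and two-sided 0.05 come from the Protocol. It gives no MAKE30 rate, so control rates of 20–70% are assumed. The low end allows for the inclusion criteria in 4.1, which start from "Hospitalized patients with ARD, will be defined as the diagnosis using the KDIGO criteria of serum creatinine" and do not require intensive care. The high end allows for the only nearby rate in the document, in 2.4: "About 50% of ICU patients with AKI die".

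**3. Formula.** With control rate p₁, treated rate p₂ and p̄ = (p₁ + p₂)/2, the uncorrected chi-square test has

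power ≈ Φ{ [ |p₁ − p₂|√n − 1.96√(2p̄(1 − p̄)) ] / √(p₁(1 − p₁) + p₂(1 − p₂)) }.

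Example, 40% vs 25%: p̄ = 0.325. The numerator is 0.15 × √55 − 1.96 × 0.6624 = 1.112 − 1.298 = −0.186. The denominator is √(0.24 + 0.1875) = 0.654. Φ(−0.284) = 0.388, so power is 39%.

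**4. Results at 55 per group** (normal approximation, except the two exact columns, which are binomial enumerations at the rounded pair):

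| Control rate | Power, 10 points | Power, 15 points | Reduction for 80% | Rounded pair | Exact power, chi-square | Exact power, Fisher |
|---|---|---|---|---|---|---|
| 20% | 31% | 67% | 16.9 points | 20% vs 3% | 85% | 75% |
| 30% | 23% | 47% | 21.0 | 30% vs 9% | 82% | 74% |
| 40% | 19% | 39% | 23.8 | 40% vs 16% | 82% | 76% |
| 50% | 18% | 35% | 25.5 | 50% vs 24% | 82% | 76% |
| 60% | 18% | 35% | 26.4 | 60% vs 34% | 78% | 71% |
| 70% | 19% | 37% | 26.2 | 70% vs 44% | 79% | 72% |

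With Fisher's exact test, power is 13–22% for 10 points and 27–57% for 15 points, and 80% needs about 18–29 points.

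**5. Size needed.** For a 15-point reduction, 80% power with the chi-square test takes 76, 121, 152, 170, 173 and 163 per group at control rates of 20% to 70%.

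**6. Precision.** If both arms share the control rate, the 95% CI half-width for the risk difference is 1.96√(2p(1 − p)/55). That is 15.0 points at 20%, 18.7 at 50% and 17.1 at 70%. At the rounded pairs, 1.96√([p₁(1 − p₁) + p₂(1 − p₂)]/55) gives 11.5 to 18.0 points.

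**7. The randomisation list.** It has 120 places, by count 59 iron and 61 placebo, against 2 × 55 = 110 calculated. With 60 per group, chi-square power is about 19–33% for 10 points and 38–71% for 15 points, and 80% needs about 16–25 points. The conclusion does not change.

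**The case against.** The arithmetic is correct for its own inputs, and no sentence claims a power for MAKE30, so no printed number is false. A trial may be sized on a secondary outcome. That is true, but the Protocol does not say that it did so, and this calculation is its only justification for the trial size.

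The 10- and 15-point effects are illustrative; the Protocol names no target. Larger effects fare better: a halving of risk has power of about 78%, 90% and 97% at control rates of 50%, 60% and 70%, though only 31%, 47% and 63% at 20%, 30% and 40%. This stands, and the detectable reduction of 17–26 points is the more neutral summary.

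The 20–70% range is wide and loosely anchored. It is an assumption, but no rate within it gives 80% power for a 15-point reduction.

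The 11.5-point half-width belongs to 20% vs 3%, where the treated arm expects only 55 × 0.03 = 1.65 events. The formula is unreliable there, and that figure is better kept out of a protocol.

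A list somewhat longer than the planned enrolment is ordinary practice and contradicts nothing. It is a minor point, but one sentence would settle what the planned total is.

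Nothing in the Protocol says that a null result will be read as no effect. The risk of misreading is a judgement; the mismatch between calculation and endpoint is not.

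**Conclusion.** The concern holds. The sample size of 55 per group rests on a continuous variable that is not named, while the primary endpoint is a proportion with no stated rate, target difference or power. The implied 80% power does not carry over.

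Under assumed control rates of 20–70%, with 55 per group and an uncorrected chi-square test at two-sided 0.05, the trial has 80% power only for absolute MAKE30 reductions of about 17–26 points. A true 10-point reduction would be non-significant in 69–82% of such trials. A true 15-point reduction would be non-significant in 53–65% at control rates of 30% or more, and in 33% at 20%. Fisher's test raises these proportions. The mismatch itself depends on no assumption; only its size does. It must be corrected, because the reading of the primary result depends on it.

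**What to change.** Rewrite the sample-size paragraph in Design of the Study, leaving the number per group and the endpoint alone:

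1. Name the variable and unit behind the 0.8 difference and the SD of 1.5.
2. Say that 55 per group was not derived for MAKE30.
3. State what 55 per group can detect, with the rates marked as assumptions. Suggested text:

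> With 55 per group and two-sided 0.05, the uncorrected chi-square test has about 80% power (exact 78–85%) for MAKE30 of 20% vs 3%, 30% vs 9%, 40% vs 16%, 50% vs 24%, 60% vs 34% or 70% vs 44%. With Fisher's exact test, power at these pairs is 71–76%. If both arms share the control rate, the expected 95% CI half-width for the risk difference is 15–19 points. A non-significant result will not be read as no effect.

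   If the sponsor can justify one expected control rate from outside the trial, that rate with its detectable difference can replace the list.
4. Say how the 120 list places (59 iron, 61 placebo) relate to the 110 calculated.

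Mark the restatement as made after the August 2022 start, and do not take the assumed rates from unblinded trial data.

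The cost is an amendment to one paragraph and a less favourable stated power: the trial is then openly informative only for large MAKE30 effects. No patients are added and no endpoint changes. The amendment discloses the limit and does not remove it.

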## Old Civil Hospital of Guadalajara "FRAY ANTONIO MAYOR"

Teaching Subdirectorato  
Research Coordination

The randomization process by random assignment was carried out with the  
tool INCI Clinical Trial Randomization Tool:

<https://ctrandomization.cancer.gov/>

Sequences have been generated for each arm and stratum of  
your trial using maximum asymptotic randomization.

group	Subject	Assignment	Assigned Arm Index
all	1	placebo	2
all	2	Dextran Iron	1
all	3	Dextran Iron	1
all	4	placebo	2
all	5	Dextran Iron	1
all	6	placebo	2
all	7	placebo	2
all	8	Dextran Iron	1
all	9	placebo	2
all	10	Dextran Iron	1
all	11	Dextran Iron	1
all	12	placebo	2
all	13	Dextran Iron	1
all	14	Dextran Iron	1
all	15	placebo	2
all	16	Dextran Iron	1
all	17	Dextran Iron	1
all	18	placebo	2
all	19	placebo	2
all	20	Dextran Iron	1
all	21	Dextran Iron	1
all	22	placebo	2

Version 2.0, 29 June 2023

---

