#### **Exploratory objectives:**

- safety of intravenous iron administration compared to placebo: assessed by the occurrence of adverse events such as allergic reaction, hypotension, dyspnea, rash, erythema. These will be evaluated during

[name] [contact], [name] GUADALAJARA, JAL

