## *Old Civil Hospital of Guadalajara* "FRAY ANTONIO MAYOR"

---

drug administration and during hospitalization frequently every 24 hours by the nephrology staff, including the study investigators.

Version 2.0, 29 June 2023

Effect of intravenous iron repletion on renal function in patients with iron deficiency and acute kidney injury, clinical trial. June 2023, HCG/CEI-1232/22

[name] [contact], [name] GUADALAJARA, JAL

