## Old Civil Hospital of Guadalajara "FRAY ANTONIO MAYOR"

Teaching Subdirectorato  
Research Coordination

all	94	placebo	2
all	95	placebo	2
all	96	placebo	2
all	97	placebo	2
all	98	Dextran Iron	1
all	99	Dextran Iron	1
all	100	placebo	2
all	101	Dextran Iron	1
all	102	placebo	2
all	103	Dextran Iron	1
all	104	Dextran Iron	1
all	105	placebo	2
all	106	placebo	2
all	107	placebo	2
all	108	Dextran Iron	1
all	109	placebo	2
all	110	Dextran Iron	1
all	111	Dextran Iron	1
all	112	placebo	2
all	113	Dextran Iron	1
all	114	Dextran Iron	1
all	115	placebo	2
all	116	placebo	2
all	117	Dextran Iron	1
all	118	Dextran Iron	1
all	119	placebo	2
all	120	placebo	2

Version 2.0, 29 June 2023

, and members of the nephrology staff, blinded to the allocation groups, administered the drugs to each patient every day.

All patients will have a detailed medical history and physical examination. Complete blood count, serum creatinine, serum urea, serum urea nitrogen, serum electrolytes, and blood test parameters were measured daily.

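### The protocol prints the arm for all 120 subject numbers in a version dated within the study period, and its blocks of five contradict both the named method and the list

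*Protocol*

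**What the plan says.** Section 2 (Design of the study) describes a placebo-controlled trial with "randomization method in blocks of 5 by frequency of occurrence". A page later it says the sequence came from an online randomization tool, in a sentence that begins "Sequences have been generated for each arm and stratum of" and continues "your trial using maximum asymptotic randomization".

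The list follows directly. It has a single stratum, labelled all, and consecutive subject numbers from 1 to 120. Each row gives the arm in words, with a numeric code under the heading "Assigned Arm Index". The pages carry "Version 2.0, 29 June 2023". Section 1.2 gives the study period as August 2022 to December 2023.

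Immediately after the last row, the text refers to "members of the nephrology staff, blinded to the allocation groups" as the people who gave the study drugs. The exploratory objectives in section 2.5 define safety as "assessed by the occurrence of adverse events such as allergic reaction, hypotension, dyspnea, rash, erythema". They have these events evaluated during drug administration and every 24 hours in hospital "by the nephrology staff, including the study investigators".

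**The concern.** Concealment requires that whoever decides on a patient's entry cannot know the next assignment. Blinding requires that whoever treats or assesses the patient cannot look up the arm. A numbered list in clear text, in the body of the protocol, removes both protections for anyone who holds the document. With one stratum and consecutive numbers, the last number used is enough to read the next arm. This is full disclosure of the sequence, not just a pattern that might be guessed.

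Two things are at stake. Enrolling staff who hold this version could admit or defer patients according to the coming arm, and blinded laboratory measurement would not repair that selection bias. Adverse events such as hypotension, dyspnea or rash are partly a matter of judgement, and the protocol gives them to nephrology staff and investigators, who may well hold the protocol. Death and the creatinine part of the primary composite are less open to assessment bias.

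A separate and lesser fault is the description of the method. Five is an odd number and cannot balance two arms 1:1 within a block. Blocks are also a different method from the one named beside the list. A report that repeated the block description would misdescribe the sequence.

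**Working it through.** **Exposure of the list**

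- Rows printed: 120. Rows with the arm legible: 120, or 100%.
- Planned size (section 2): 2 x 55 = 110, so the list covers every planned patient.
- Version date 29 June 2023; study period August 2022 to December 2023. The version therefore falls inside the period.

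The protocol does not say how many patients had been allocated by that date. As an illustration, assume even enrolment of 110 patients from 1 August 2022. Then 29 June 2023 is day 332.

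| Assumed end of enrolment | Day | Remaining = (end day - 332) / end day x 110 |
|---|---|---|
| 31 December 2023 | 517 | 185 / 517 x 110 = 39 |
| 2 October 2023 (90 days earlier, to allow the 90-day evaluation in section 2.5) | 427 | 95 / 427 x 110 = 24 |

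On these assumptions 71 to 86 patients were already allocated and 24 to 39 were not. Without them, the number of foreseeable allocations lies anywhere from 0 to 110.

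**Blocks of five against the printed list**

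Transcribing all 120 rows gives 59 iron and 61 placebo; the first 110 give 54 and 56. If the list were built in blocks of five that were as balanced as possible, each consecutive run of five would hold 2 or 3 iron. The iron counts in order are:

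3, 2, 3, 3, 2, 2, 1, 5, 1, 3, 2, 4, 2, 1, 4, 2, 3, 3, 1, 2, 3, 2, 3, 2

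| Iron in the run of five | 1 | 2 | 3 | 4 | 5 |
|---|---|---|---|---|---|
| Number of runs | 4 | 9 | 8 | 2 | 1 |

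So 9 + 8 = 17 of 24 runs fit and 4 + 2 + 1 = 7 do not. The seven are subjects 31-35, 36-40, 41-45, 56-60, 66-70, 71-75 and 91-95. Subjects 36-40 are all iron.

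A different starting point does not rescue the description. Shifting the block start by 1, 2, 3 or 4 positions leaves 6, 3, 3 and 7 of 23 complete runs that do not fit.

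**What the list does look like**

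The running difference (iron minus placebo) stays between -3 and +3. Each time it reaches 3 in either direction, the next assignment goes back toward balance. This is consistent with a maximal procedure with an imbalance limit of 3, and so with the method named beside the list. It is an inference from one realised sequence; the protocol states no limit.

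**The passages side by side**

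- Drug administrators are stated to be blinded, yet the arm of every subject number is printed just above that statement in the same document.
- Adverse events are assessed by nephrology staff and investigators, and the visible text puts no restriction on who may read the list.

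**The case against.** The strongest reply is that harm is not shown. The protocol does not say who received Version 2.0, whether version 1.0 held the list, or when the list was inserted. Parts of the text are in the past tense, so the list may have been added after most or all patients were allocated. A range of foreseeable allocations that includes zero cannot show that concealment was broken. This stands: the finding concerns what the protocol exposes, not what staff did.

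The sentence after the list has also lost its opening in the available text, and other pages were removed, so a statement about who held the allocation may be missing. No weight is placed on the absence of such a statement. Equally, no custody rule could undo a list printed in the protocol for someone who holds the protocol.

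A third point is that the stated blinding covers the staff who gave the drugs, while the adverse event assessors are not expressly called blinded. That is correct, and the overlap between the two groups is inferred. The direct conflict is between the printed list and the blinded administrators; the risk to adverse event assessment follows if the assessors hold this version.

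Finally, the block description taken alone is a minor wording error, and the timing figures rest on assumed accrual. Both points are fair. Neither affects the main finding, which depends only on the printed list and its date.

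**Conclusion.** The concern holds. The arm is printed for 120 of 120 subject numbers in a version dated within the study period, so the protocol as written leaves allocation open to anyone who holds it and conflicts with its own statement of blinding. This must be fixed, because concealment underlies every comparison between the arms and analysis cannot restore it once lost. Whether any allocation was in fact foreseen is unknown. The range is 0 to 110, and the figure of about 24 to 39 still to come on the version date rests on even enrolment from 1 August 2022 and on the two assumed end dates.

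The block description is wrong as well, though less serious. It contradicts the named method, cannot give 1:1 balance within a block, and fails in 7 of 24 consecutive runs.

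**What to change.** 1. Remove the list from the protocol and from circulated copies.
2. If patients remain to be enrolled, void the unused entries and generate a new concealed sequence for the unassigned numbers. It should be held by someone with no part in enrolment, care or outcome assessment.
3. Replace the block description with the method and settings in the randomization tool's own record. The sponsor must confirm any imbalance limit from that record and not infer it from the list.
4. In the report, state who had access to the list and from what date.
5. If enough patients were allocated from a concealed sequence, either before enrolling staff could see the list or from the new one, add a sensitivity analysis restricted to them. This group may be small.

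If enrolment is complete, only the method correction and the disclosure of access apply.

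The cost is a short amendment and a statement in the report. If enrolment is open, it also takes one new computer-generated list and an independent holder for it. No extra patients are needed.
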